After treatment discontinuation, subjects will be followed for disease progression (if progression has not already occurred) and survival. Post-treatment calls will be performed every 6 months until discontinuation from the study. Survival information (i.e., the date and cause of death, post-treatment cancer therapies, date of progression etc.) will be collected. This period will continue for 2 years following discontinuation of venetoclax.

Extended Access Phase

In countries where venetoclax is not commercially available, subjects who continue to derive benefit after 2 years of treatment may be able to extend their treatment for up to 2 additional years. If a subject in the extended access phase of this study continues to derive benefit from Venetoclax after the 2-year extension, then per PI's assessment, subjects who are transferring to the venetoclax extension study, Study M19-388, may remain in Extended Access for up to additional 1 year or until the extension study is approved and initiated at the site, whichever is sooner. AbbVie will work with the

investigator on a case by case basis to consider the potential continuation of venetoclax therapy. The Extended Access Visits will include:

- Collection of Survival information
- AE/SAE/Con Med assessment
- Study drug reconciliation and dispensing

All other procedures should be performed as standard of care. The specific study assessments to be performed during these visits are detailed in [Appendix E Study Activities](#).

Assignment of Subject Numbers

Subjects will be assigned unique consecutive subject numbers at screening, as described in Section 5.5.3. The results of all screening evaluations must be within clinically acceptable limits, upon review by the investigator before a subject can be administered study drug. Subjects will not be enrolled in the study if laboratory or other screening results are unacceptable.

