5.4 Removal of Subjects from Therapy or Assessment

5.4.1 Discontinuation of Individual Subjects

Each subject has the right to withdraw from the study and/or study drug treatment at any time. In addition, the investigator may discontinue a subject from study drug treatment at any time if the investigator considers it necessary for any reason including:

- The investigator believes it is in the best interest of the subject
- Subject's response to therapy is unsatisfactory, as evidenced by progression of disease while on study drug
- The subject requires other cancer treatment (e.g., radiotherapy, cancer-related surgery as a result of tumor progression, alternate anti-neoplastic agents) during the study period
- unacceptable toxicity
- The subject becomes pregnant while on the study

- drug/protocol non-compliance

The investigator will inform AbbVie prior to discontinuing a subject from the study by contacting the Clinical Team Leader as identified in Section 7.0. All subjects will be included for analysis of safety data. Subjects who withdraw from the study will not be replaced unless they are not evaluable.

Subjects will continue to be followed for unresolved AEs and survival information for any subject who has not experienced PD at the time of venetoclax discontinuation.

Final Visit

Upon study drug discontinuation and/or upon discontinuation from the study, the reason(s) for discontinuation will be recorded in electronic case report forms (eCRFs) and a final visit will be performed. The final visit procedures as listed in [Appendix D](#) should be performed as soon as possible after discontinuation from study drug.

30-Day Safety Follow-Up Visit

A 30-Day Safety Follow-up Visit should be performed approximately 30 days (\pm 3 days) following the last dose of venetoclax. The 30 day safety follow up procedures listed in [Appendix D](#) should be performed.

Post Treatment and Survival Follow-Up Calls

For subjects who discontinue venetoclax therapy, but do not discontinue the study, post treatment follow-up calls will be performed every 6 months (\pm 7 days) for survival information (i.e., disease progression, the date and cause of death, post-treatment cancer therapies, etc.) and will be collected via telephone calls for a period of 2 years and recorded in the eCRFs.

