Progression-free survival (PFS) will be defined as the number of days from the date of first dose to the date of earliest disease progression or death. All disease progression will be included regardless whether the event occurred while the subject was taking the study drug or had previously discontinued the study drug. If the subject does not experience disease progression or death, then the data will be censored at the date of last disease

assessment. Data for subjects who receive non-protocol CLL therapy prior to disease progression will be censored at the last disease assessment prior to receiving non-protocol therapy. Data for subjects without any disease assessments performed after the baseline visit will be censored at the time of enrollment plus 1 day. PFS will be analyzed by Kaplan-Meier methodology using data for all subjects enrolled. Median time PFS will be calculated and 95% confidence interval for median time PFS will be presented.

Overall survival (OS) will be defined as number of days from the date of first dose to the date of death for all dosed subjects. For subjects who did not die, their data will be censored at the date of last study visit or the last known date to be alive, whichever is later. OS will be analyzed by Kaplan-Meier methodology using data from all enrolled subjects. Median time survival will be estimated and 95% confidence interval for the median time survival will be presented.

The CR rate (CR + CRi) in previously treated BCRi subjects will be assessed based on the 2008 Modified IWCLL NCI-WG criteria. The ninety-five percent (95%) confidence interval based on binomial distribution will be constructed for the calculated CR rate.

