Overall survival (time to death) for a given subject will be defined as the number of days from the first dose date of venetoclax to the date of the subject's death (i.e., $OS = death/censoring\ date - first\ dose\ date + 1\ day$). All events of death will be included, regardless of whether the event occurred while the subject was still taking any study drug, or after the subject discontinued any study drug. If a subject has not died, then the data will be censored at the date when the subject was last known to be alive prior to the cutoff date. The date of the last known to be alive will be determined by selecting the last available date of the following study procedures for a subject: study visit/contact date, tumor assessment, clinical disease progression, physical examination, vital signs assessment, clinical laboratory collection, study drug, adverse event assessment, concomitant medication assessment, drug or study completion, survival visit, and post treatment therapy assessment. The distribution of the time to death will be estimated

using Kaplan-Meier methodology. Median survival time and the corresponding 95% confidence interval will be estimated.

Minimal Residual Disease (MRD) Response Rate

The rate of MRD response in CLL subjects will be defined as the proportion of CLL subjects who achieved MRD negative status with less than one CLL cell per 10,000 leukocytes (or below 10^{-4}). All subjects with an MRD assessment will be included in the denominator for the calculation of MRD response rate. Minimal residual disease response will be summarized by categories: MRD negative, MRD positive, or MRD unknown/missing. The 95% confidence intervals based on the binomial distribution (Clopper-Pearson exact method) will be provided.

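### SAP 10.1.1 lets a study completion date fix the overall survival censoring date without requiring that the subject was known to be alive on that date

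*SAP*

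**What the plan says.** SAP 10.1.1 (Overall Survival) says that a subject who has not died is "censored at the date when the subject was last known to be alive prior to the cutoff date". The next sentence turns this into a derivation: the date is "determined by selecting the last available date of the following study procedures for a subject". The list covers visits and contacts, tumour assessment, clinical progression, examination, vital signs, laboratory samples, study drug, adverse events and concomitant medication, and ends with "drug or study completion, survival visit, and post treatment therapy assessment". It sets no vital-status condition and makes no exception for subjects lost to follow-up.

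Protocol 8.1.2.2 has surviving subjects "censored at the date of last study visit or the last known date to be alive, whichever is later". It does not name study completion as a source.

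Off drug, after the 30-day safety visit, survival information comes by telephone. Protocol 5.3.1.1: "Post-treatment calls will be performed every 6 months until discontinuation from the study" and "This period will continue for 2 years following discontinuation of venetoclax". Protocol 5.4.1 has the same six-month interval.

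SAP 6.4 has a separate rule. Subjects with a missing progression date, death date or last-known-alive date are treated as censored in the time-to-event analyses, at the interim data cutoff date.

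**The concern.** A Kaplan-Meier curve should count a subject as at risk only while a death would have been recorded had it occurred. Most items on the SAP list meet that test, because a living subject had to be seen, sampled or spoken to. A study completion record need not. Protocol 6.1.1.1 and 6.1.2.1.1 use the Study Completion eCRF to record discontinuation for progression and deaths from CLL, so it is a status form rather than a procedure on a living subject.

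With calls six months apart, a lost subject may be recognised only after a missed call. If the form is dated when the site closes the case, the derivation takes that later date and adds person-time in which no death could be observed.

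What is at stake is the overall survival curve. It is one of the key secondary endpoints in Protocol 8.1.2.2. The trial has one arm, so no comparator shares the error, and SAP 10.1 plans no efficacy testing, so the estimate and its interval are the whole result.

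**Working it through.** **No figure to reproduce.** The documents state no overall survival rate, death count or loss rate. The check therefore covers which records can drive the rule, the direction of the effect, and its size under stated assumptions.

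**1. When the completion date matters.** The rule takes a maximum. Visits, contacts, samples and dosing dates are on the list, so a completion date changes the result only when it is later than all of them. That is the case in which no other listed record supports that the subject was alive.

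**2. Direction and size.** Assume deaths at constant rate λ, independent loss at constant rate ν, and each lost subject kept at risk for g months after last contact. The ratio of unobservable to observable subjects at risk at time t is

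r(t) = [ν/(λ+ν)] × [exp((λ+ν)·min(t, g)) − 1],

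and the Kaplan-Meier hazard becomes λ/(1+r(t)). Since r cannot be negative, survival can only be raised. With g = 0, r = 0 and there is no bias.

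Example (assumed): true 24-month survival 80%, 10% lost by 24 months, g = 6 months.
- λ = −ln(0.80)/24 = 0.009298 per month; ν = −ln(0.90)/24 = 0.004390 per month.
- From month 6 on: r = (0.004390/0.013688) × [exp(0.013688 × 6) − 1] = 0.3207 × 0.0856 = 0.02745.
- Effective months at risk: 6 × 0.9867 (mean of 1/(1+r) over months 0 to 6) + 18/1.02745 = 5.920 + 17.519 = 23.439.
- Survival = exp(−0.009298 × 23.439) = 80.42%, an excess of 0.42 points.

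Simulation (n = 250, 3,000 runs) gave 80.47% with the gap and 79.94% without, each with a simulation error of about 0.05 points. The standard deviation of one 24-month estimate was about 2.5 points.

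Excess in 24-month survival, percentage points:

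| True survival | Lost by 24 months | g = 1 | g = 3 | g = 6 | carried to month 24 |
|---|---|---|---|---|---|
| 90% | 2% | 0.01 | 0.02 | 0.04 | 0.10 |
| 80% | 5% | 0.04 | 0.11 | 0.20 | 0.49 |
| 80% | 10% | 0.08 | 0.22 | 0.42 | 0.98 |
| 80% | 20% | 0.16 | 0.47 | 0.88 | 2.00 |
| 70% | 20% | 0.23 | 0.66 | 1.25 | 2.93 |

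**3. Loss only after stopping drug.** A second simulation assumed 250 subjects, 14 months of accrual, cutoff about 11 months after the last subject, discontinuation 0.3 per year, deaths 0.05 per year on drug and 0.3 to 0.6 off drug, 20 to 40% of off-drug subjects lost, and a gap of 6 or 12 months. Survival at 23 months was 0.3 to 1.3 points higher than with censoring at last contact. With last contact set one month after stopping drug, the range was 0.3 to 1.5. The standard error there was 3.3 to 3.9 points, with about 25 subjects at risk.

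**4. SAP 6.4 beside SAP 10.1.1.** Every treated subject has a study drug date, which is on the 10.1.1 list, so a date derived by that list is never missing. The 6.4 branch for a missing last-known-alive date is then redundant or refers to another variable. The missing-death-date branch, read literally, covers every survivor as well as a known death with an unknown date. Placing any of these at the cutoff extends survival time past the last evidence of life and conflicts with 10.1.1. The last column of the table shows the scale if all lost subjects were carried to the horizon.

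**The case against.** The governing sentence in SAP 10.1.1 is right: it asks when the subject was last known to be alive, and an administrative closure date would contradict it. Protocol 5.4.1 also calls for a final visit on discontinuation of drug or study, so completion is normally tied to a contact. Protocol 8.1.2.2 does not define its last-known-alive date and Protocol 8.1 leaves detail to the SAP, so the two rules are not in direct conflict. All of this stands. It narrows the problem to subjects who cannot be reached, but the sentence a programmer will implement is the mechanical one, and it has no guard for them.

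A reader might infer that lost subjects are in fact carried alive past last contact and that overall survival is biased. The documents do not support that: they do not say what date is entered for a lost subject, or that any were lost. Nor is a survival-visit date suspect in itself. A call that finds the subject alive is sound evidence, and nothing says that a failed call creates a dated record.

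The effect is also small beside the sampling error. In the second simulation survival stays well above 50% at 23 months, so the planned median is not reached by then under either rule; only the curve moves.

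Finally, censoring at last contact is not unbiased when loss falls on subjects at higher risk of death. In the same simulations it exceeded the no-loss estimate by roughly 1 to 5 points, more than the effect at issue. That stands, and the change below does not address it.

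**Conclusion.** The overall survival derivation is under-specified in a way that can err only upward. Followed as written for a lost subject whose completion record is dated after the last real contact, it gives a wrong censoring time. Whether this happens depends on a dating convention and a loss rate that the documents do not give. Under the assumed ranges the excess is about 0 to 1.3 points at roughly two years, 1.5 in the harsher variant, and exactly zero where completion date and last contact coincide. It concerns an untested secondary endpoint and does not touch the primary complete remission rate.

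The cutoff-date rule in SAP 6.4 is the more explicit departure from last evidence of life. It may be meant only for a few incomplete records, and the text does not show that all survivors are to be censored at the cutoff. It still needs to be squared with 10.1.1. The correction is worth making because it is nearly free and removes a one-directional error.

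**What to change.** In SAP 10.1.1, add that a study completion date, or a survival-visit record, counts towards the last-known-alive date only where contact with the subject or status alive is documented for that date. Otherwise, including loss to follow-up and administrative closure, censor at the last actual contact.

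In SAP 6.4, say which subjects the cutoff-date rule covers for overall survival and align it with 10.1.1, so that no subject is censored later than the last evidence of life. State separately how a known death with a missing date is handled.

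The cost is one sentence in 10.1.1, the matching edit in 6.4, and one programming condition on discontinuation reason and survival status. SAP 7.0 already summarises the primary reason for study discontinuation from the eCRF. Overall survival may look slightly less favourable. Reporting the number of subjects lost and the time from last contact to completion date would show whether the issue arose, and would help readers judge the bias from death-related loss that remains.

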Venetoclax will be administered orally once daily (QD), continuously. Venetoclax tablets should be taken with a meal and water in the morning at approximately the same time each day. To mitigate the risk for TLS, the first 5 weeks of treatment include a dose-titration phase where venetoclax will be dosed in increments as outlined in [Figure 1](#). The

starting dose of venetoclax is 20 mg once daily. The dose will be gradually increased over a period of 5 weeks up to the daily dose of 400 mg.

Figure 1. 5-Week Dose-Titration Schedule

Week	VENETOCLAX Daily Dose
1	20 mg
2	50 mg
3	100 mg
4	200 mg
5 and beyond	400 mg

Disease response will be assessed by the investigator based on laboratory results and physical examinations using the 2008 Modified International Workshop on CLL National Cancer Institute – Working Group (IWCLL NCI-WG) Guidelines for Tumor Response with the addition of CT imaging (or MRI). A Disease Assessment for clinical response by physical exam and hematologic assessments will be performed at Screening, Week 24, Week 36 and Week 48. To confirm the response, a CT scan (or MRI if CT is medically contraindicated) will be performed at Week 48 on all subjects and BM samples will be collected for subjects with CR to confirm the response.

MRD assessments will be performed by using peripheral blood specimens at Week 1 Day 1 (baseline), Week 24 and Week 48. When confirming a CR status or complete remission with incomplete bone marrow recovery (CRi) status per IWCLL NCI-WG guidelines with a bone marrow aspirate and biopsy, MRD assessment of the bone marrow aspirate should also be performed.

Quality of life will be assessed by using the following patient reported outcome questionnaires: the EQ-5D-5L, the FACT-Leu, and the FACIT-F. Quality of life endpoints will be summarized based on the scoring manual for the instruments.

Subjects may continue to receive venetoclax for up to 2 years provided they continue to tolerate the drug, have no evidence of disease progression (based on investigator's assessment), do not have unacceptable toxicity and do not meet any of the criteria for discontinuation (see Section 5.4.1). A final visit will be conducted upon treatment discontinuation.

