8.1.2.3 Exploratory Efficacy Endpoints

The rate of MRD negativity in subjects will be summarized. This rate will be defined as the proportion of subjects who had MRD negativity status. Ninety-five percent (95%) confidence intervals based on the binomial distribution will be provided. In addition, the relationship between venetoclax PK and efficacy parameters including MRD level and CR will be evaluated.

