5.0 Analysis Populations

5.1 Definition for Analysis Populations

5.1.1 Efficacy Populations

5.1.1.1 Intent-to-Treat (ITT) Population

All enrolled subjects treated with at least one dose of venetoclax will be included in the ITT population. Efficacy analyses will be performed on the ITT population, unless otherwise specified.

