10.2.3 Exploratory Efficacy Analysis

The rate of MRD negativity in subjects will be summarized. This rate will be defined as the proportion of subjects who had MRD negativity status in peripheral blood. Ninety-five percent (95%) confidence intervals based on the Clopper-Pearson exact method for binomial distribution will be provided.

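### The SAP does not fix the denominator of the exploratory MRD-negativity rate; if only post-baseline samples count, early stoppers drop out and the rate exceeds the all-treated rate

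*SAP*

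**What the plan says.** The denominator rule is in SAP 10.1.1, under the MRD response rate: "All subjects with an MRD assessment will be included in the denominator for the calculation of MRD response rate". The next sentence adds a three-way summary: "Minimal residual disease response will be summarized by categories: MRD negative, MRD positive, or MRD unknown/missing". The interval is Clopper-Pearson. No time point is given.

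Other places bear on the denominator:

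- SAP 10.2.3 defines the rate again, without the restriction: "This rate will be defined as the proportion of subjects who had MRD negativity status in peripheral blood". Protocol 8.1.2.3 likewise has "the proportion of subjects who had MRD negativity status".
- SAP 5.1.1.1 sets the default: "Efficacy analyses will be performed on the ITT population, unless otherwise specified". ITT there means enrolled and dosed at least once. Protocol 8.1 has a similar default, all enrolled subjects.
- Protocol 5.1 gives the sampling times: "MRD assessments will be performed by using peripheral blood specimens at Week 1 Day 1 (baseline), Week 24 and Week 48". The baseline sample is thus itself called an MRD assessment.
- Protocol Appendix D shows blood MRD at Week 1 Day 1, Week 24 and Week 48, and none at the Final Visit. Appendix F adds one blood sample when CR or CRi is confirmed.
- For CR + CRi and for ORR, SAP 10.1.1 classes subjects who do not achieve the response as non-responders.

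**The concern.** The usual meaning of an MRD assessment, in a rate that measures response, is a sample taken after treatment has begun. On that meaning, a subject who progresses, dies or stops before Week 24 has no planned post-baseline blood sample and is not counted at all. The one blood sample outside the fixed visits is triggered by a suspected complete remission. Being sampled is therefore tied to how the subject fares, at least in part, by the visit schedule itself.

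The result would be a rate conditional on staying long enough to be sampled, reported in the same study as CR and ORR rates that keep every treated subject. SAP 10.4 also tabulates MRD response by CR, PR and non-responder, and early stoppers without a sample would probably be lost mostly from the last group.

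On the other meaning, where baseline counts, nearly everyone is in the denominator. One sentence thus allows two different rates, and the choice would fall to whoever programs the table, possibly after the data are known.

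**Working it through.** **Inputs.** The documents state no MRD rate, no MRD sample size and no fraction without a sample, so there is no figure of the plan's own to reproduce. From the documents: about 250 subjects in total and 190 BCRi-naive (SAP 4.2 and 4.3), and Clopper-Pearson 95% intervals (SAP 10.1.1). Assumed for illustration: 30% of treated subjects MRD-negative (75 of 250, or 57 of 190), and m, the fraction of treated subjects with no qualifying sample, from 0 to 30%.

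**Formula.** Let N be the number treated, n = N(1 − m) the number with a qualifying sample, and x the number MRD-negative. A negative result needs a sample, so x is the same under either denominator.

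- All-treated rate, with missing counted as not negative: x/N.
- Sampled-only rate: x/n = (x/N) × 1/(1 − m).

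The sampled-only rate can never be the lower of the two, and the relative excess depends on m alone.

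**Results for N = 250 and x = 75** (all-treated rate 75/250 = 30.0%, 95% CI 24.4 to 36.1):

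| m | n | Sampled-only rate | 95% CI | Ratio N/n |
|---|---|---|---|---|
| 0 | 250 | 75/250 = 30.0% | 24.4–36.1 | 1.00 |
| 5% | 238 | 75/238 = 31.5% | 25.7–37.8 | 1.05 |
| 10% | 225 | 75/225 = 33.3% | 27.2–39.9 | 1.11 |
| 20% | 200 | 75/200 = 37.5% | 30.8–44.6 | 1.25 |
| 30% | 175 | 75/175 = 42.9% | 35.4–50.5 | 1.43 |

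In the 5% row, n is 237.5 rounded to 238.

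The m = 0 row is also the answer if the baseline sample qualifies and every treated subject gave one.

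The pattern in the BCRi-naive group is the same: 57/190 = 30.0% (23.6–37.1) of all treated, against 57/152 = 37.5% (29.8–45.7) among those sampled at m = 20%.

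**Who is lost.** If the rate is taken at any time after baseline, only subjects with no post-baseline sample leave. A subject sampled at Week 24 who progresses afterwards stays in. If the rate is taken at Week 48 alone, those without a Week 48 sample leave as well, so m is at least as large. The SAP does not say which applies.

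**The case against.** A reader might infer that the SAP has chosen a biased denominator and that the reported rate is certainly inflated. The text does not go that far. It says neither only nor post-baseline, a baseline MRD sample is planned for every subject, and the unrestricted definitions in SAP 10.2.3 and Protocol 8.1.2.3 are compatible with an all-treated rate. On that reading there is essentially no inflation. This stands, and it is why the point is an unsettled denominator, with upward bias on one reading.

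A reader might also infer that the category list "MRD negative, MRD positive, or MRD unknown/missing" contradicts the denominator rule. It need not. A subject can have an unusable assay, a baseline sample and no later one, or a Week 24 result with Week 48 missed. If subjects without a result are displayed there, readers could even recompute the rate. What remains open is whether that category is counted in the denominator.

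Nor do the documents show that missing samples are concentrated in subjects doing badly. The schedule makes early stopping an obvious route to having no sample, but laboratory and shipping failures are others, and no frequencies are given.

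It can fairly be added that SAP 10.1.1 never states in so many words that missing counts as non-response for CR and ORR; that is a natural inference from its non-responder rule. MRD is exploratory, SAP 10.1 plans no efficacy testing, and there is no comparator arm. These facts limit the consequences. They do not settle which denominator will be used.

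**Conclusion.** The point holds as a denominator left open between two materially different rates. If a post-baseline sample is required, the SAP's rate exceeds the all-treated rate by 1/(1 − m): about 11% in relative terms at m = 10%, 25% at 20% and 43% at 30%. If the baseline sample qualifies and was taken from everyone, the excess is nil. The documents do not fix m, so the tabulated rates show a range and are not a forecast. They rest on the assumed 30% negativity and on taking the all-treated rate, with missing counted as not negative, as the reference. The relative excess does not depend on the assumed 30%.

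The consequence is confined to an exploratory endpoint. The primary CR + CRi analysis and its sample size are untouched.

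**What to change.** Amend the MRD paragraph in SAP 10.1.1, and align 10.2.3 with it, to state that:

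- the main MRD-negativity rate in peripheral blood is calculated on ITT, ITT-BN and ITT-BE;
- it refers to a named time point, or to the best post-baseline result;
- missing or unknown post-baseline MRD counts as not negative, and the baseline sample does not count as a post-baseline result;
- the rate among subjects with a post-baseline result is reported as supportive, with the number missing beside it.

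This is an edit to the SAP text and needs no new visit, sample or data. Its cost is that the headline rate may be lower than a sampled-only rate, and that subjects whose sample failed for technical reasons are counted as not negative. The supportive rate and the count of missing results let a reader judge how much that matters.
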